- Summary of Patient Eligibility Criteria

Women exposed to Repatha during pregnancy and their infants through the first year of life who consent to provide their information to Amgen.

- Follow-up

If the pregnant women consent for follow-up, then Amgen will follow-up with the pregnant women from the time they are exposed to Repatha through the pregnancy outcome and their infants will be followed through the first year of life.

- Variables

Outcome Variable(s): The outcomes for the study include occurrence and dates of pregnancy and maternal complications, pregnancy outcomes, and infant outcomes based on self-report. Pregnancy outcomes include the number of cases reporting live full-term births, spontaneous abortion, elective abortion, fetal death/stillbirth, and premature delivery. Infant outcomes are the number of cases reporting adverse events including complications, medical problems or congenital anomalies at birth and the number of cases reporting adverse events at 6 months and 12 months which may include whether they have not followed growth curves or met development milestones as expected for chronological age.

Exposure Variable(s): The period defining exposure to Repatha during pregnancy will be any number of days, at any dose, and at any time from up to 90 days pre-LMP, through the first day of the last menstrual period (LMP) and up to and including the end of pregnancy. Identification of pregnancy will be via postmarketed reporting through Amgen's Global Safety Database.

Other Covariate(s): Other covariates will be included which pertain to maternal information, exposure and pregnancy and delivery. Maternal covariates include demographic information for the mother, pregnancy history; medical history; other relevant history that may impact the pregnancy (family history, mother's occupation). Variables related to exposure include current medication and dates of use (prescription and over-the-counter [OTC]); and occurrence and dates of current pregnancy complications. Characteristics of pregnancy and delivery such as maternal conditions, birth information, delivery details, and newborn complications.

- Study Sample Size

Sample size will not be pre-determined. This is a descriptive study which will identify the number of pregnant women exposed to Repatha through the Amgen Global Safety Database.

- Data Analysis

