8.2.5 Study Follow-up

If pregnant women consent, they will be followed from the later date of the first day of their LMP or the date of their exposure to Repatha (index date) through the pregnancy and birth. A postpartum follow-up will occur approximately 6 to 8 weeks after delivery. Additional follow-up will occur when the infant is 6 and 12 months of age.

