8.3.2 Outcome Assessment

Pregnancy outcomes include the number of women reporting pregnancy or maternal complications, as well as, the number reporting:

- Live full-term births
- Spontaneous abortion defined as non-deliberate fetal death which occurs prior to 20 completed weeks post-LMP
- Elective abortion defined as deliberate termination of pregnancy at any time in gestation
- Fetal death/Stillbirth defined as non-deliberate fetal death anytime in gestation at or after 20 completed weeks post-LMP
- Premature delivery defined as live birth prior to 37 weeks gestation as counted from LMP (eg, ultrasound adjusted date or Ballard's score)

Outcomes related to pregnancy and maternal complications will be assessed with a Pregnancy Questionnaire (a sample form included in [Appendix C](#)). Outcomes for live births will be assessed with a Post Due Date Questionnaire (a sample form included in [Appendix D](#)) from the Amgen Global Safety Database.

The number of infants with adverse events including complications, medical problems or congenital anomalies at birth will be assessed with a Post Due Date Questionnaire (a sample form included in [Appendix D](#)) from the Amgen Global Safety Database.

Major malformations or birth defects are defined as abnormalities incompatible with life or requiring medical/ surgical intervention. The term minor birth defect generally refers to minor physical anomalies with less clinical importance that represent deviations from what is considered normal and do not have obvious medical, surgical, or cosmetic consequences. Major birth defects identified up to 1 year of age by the mother or the healthcare provider will be included in the primary analysis. Major structural birth defects may be reported by the mother, a family member or her or her child's HCP via medical records. If a major malformation is reported the medical record will be adjudicated by a physician with expertise in teratology, pediatrics, and dysmorphology. Defects will be

classified using the Center for Disease Controls (CDC) criteria (CDC 2017.:
<https://www.cdc.gov/ncbddd/birthdefects/macdp.html>).

Infant outcomes are the number of cases reporting adverse events at 6 months and 12 months and may include whether they have not followed growth curves or met development milestones as expected for chronological age. These outcomes will be assessed with an Infant Questionnaire (a sample form included in [Appendix E](#)).

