8.7.2.3.3 Analysis of the Primary, Secondary, and Exploratory Endpoint(s)

All analyses will be descriptive. These cases constitute a case series, thus line listings of pregnancy and maternal complications, pregnancy outcomes, infant outcomes and adverse events will be summarized along with tabulations of the numbers and frequencies of events by category of report: numbers who did not provide consent for follow-up, timing of exposure (first, second, or third trimester), and indication for use of the medication. Collection of exposure and outcome information in this group provides additional evidence on the safety of Repatha use during pregnancy. The denominator is the number of pregnant women exposed to Repatha during pregnancy and the numerator is the number with the outcome.

The proportion of infants with adverse events including complications, medical problems or congenital anomalies at birth will be assessed in infants of women exposed to Repatha during pregnancy with corresponding 95% confidence intervals. The proportion of infants with adverse events at 6 months and 12 months of age will be assessed. All adverse events among mothers who have received Repatha at any time during the pregnancy will be summarized including the proportion with pregnancy and maternal complications. To assess events in the developing fetus and neonate in women exposed to Repatha during pregnancy, the proportion of pregnancies resulting in spontaneous abortions, elective abortions, fetal death/ stillbirths and premature delivery will be presented, along with corresponding 95% confidence.

If the available safety information relevant to exposure during pregnancy represents a safety signal, the signal will be further evaluated through the Amgen safety governance structure and, if deemed necessary, escalated for consideration of changes to the Reference Safety Information (eg, USPI) as well as other forms of risk communication (eg, Dear Healthcare Provider Letters).

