6 TO 8 WEEKS POST DUE DATE QUESTIONNAIRE (MOTHER)

Section 1 – Reporter Information

Reporter: Mother Health Care Professional Other _____

Any change in the reporter contact information? Yes No If yes, please provide updated contact information:

Name _____ Phone () _____ Fax () _____

Email _____ Address _____ City _____

State/Province _____ Zip/Postal Code _____ Country _____

Section 2 – Mother Prenatal Medication History

Please provide any additional medication information for medicines used during your pregnancy not previously reported. For example, if you resumed or discontinued the Amgen Product or any other medications during the pregnancy (include vitamins, folic acid, herbal medications, and vaccines).

Medications/Drugs	Dose	Route (e.g. oral, subcutaneous)	Frequency (e.g. daily, weekly)	Date Drug Started (dd/mm/yy)	Date Drug Stopped (dd/mm/yy)	Indication for Treatment

Section 3 – Mother Pregnancy Complications and/or Adverse Event Information

Pregnancy Complication or Adverse Event (e.g. preeclampsia, gestation diabetes)	Date the Complication or Event Started (dd/mm/yy)	Date the Complication or Event Resolved (dd/mm/yr)	Outcome (for example: resolved, not resolved, unknown, other, etc.)

Amgen Proprietary - For Internal Use Only

6 to 8 Weeks Post Due Date Questionnaire (Mother)

Version 1. Effective: 16 September 2015

Page 1 of 2

Safety Database # [case_id]

6 TO 8 WEEKS POST DUE DATE QUESTIONNAIRE (MOTHER) *continued*

Section 4 – Mother Current Pregnancy Outcome (if applicable)

Date pregnancy ended: _____ Weeks of pregnancy at delivery (or if the outcome was a
Day Month Year loss of pregnancy): _____ weeks

Pregnancy Outcome (please check the appropriate box below)

- Live birth
 - Number of infants _____ (1: single, 2: twins, etc.)
(If multiple births: Please provide all information for each infant in the additional information text box below:)
- Pregnancy loss (miscarriage)
- Stillbirth
- Termination
 - Due to health issue (mother or baby)
 - For voluntary reason
 - Other (please specify): _____

If live birth: Gender: Male Female

Length: _____ cm/inches Birth weight: _____ gram/lb Head circumference: _____ cm/inches

Did the baby have any complications/medical problems/congenital anomalies (birth defects)? Yes No

If yes, please provide specific information below.

Additional Information on pregnancy outcome:

Section 5 – Reporter Signature

Signature of person completing questionnaire: _____ Date: _____

Please print name: _____

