Appendix E. 6- and 12-month Infant Questionnaire

Mother Safety Database #	
Infant Safety Database #	

SIX AND TWELVE MONTH
INFANT QUESTIONNAIRE

From: {Title} {First Name} {Last Name} {Company Name} {Country}	[today]
To:[reporter_first_name:corresp_contact] [reporter_last_name:corresp_contact]	

Event: Pregnancy	Product: [product_name]:[1]
AER#: [case_id]	Reply Due By: {Due Date}

Dear [reporter_first_name:corresp_contact] [reporter_last_name:corresp_contact],

Thank you for reporting your [patient_initials] pregnancy while on [product_name:first_suspect] ([generic_name:first_suspect]) therapy. Please send the completed questionnaire with requested information to the address, email or fax below.

Kindly note the following attachments:

- **SIX AND TWELVE MONTH INFANT QUESTIONNAIRE**

Respectfully Yours,

{Title} {First Name} {Last Name}
{Company Name} {Country}
Email: {email}
Fax: {fax}
Phone: {phone}

SIX AND TWELVE MONTH INFANT QUESTIONNAIRE

Mother Safety Database #

Infant Safety Database #

You may return completed form to Amgen Office Fax or Email:

Section 1 – Reporter Information

Reporter: Mother Father Health Care Professional (HCP) Other _____

Section 2 – Infant Healthcare Provider (HCP) Information

May Amgen contact the HCP for medical information regarding your child? Yes No

If yes, please provide contact information:

Name _____ Phone () _____ Fax () _____

Email _____ Address _____ City _____

State/Province _____ Zip/Postal Code _____ Country _____

Section 3 – Infant Medical Health Information

List any other medications/drugs (include vitamins and over-the-counter medications taken by the child)

Medications/Drugs	Dose	Route (e.g. oral, subcutaneous)	Frequency (e.g. daily, weekly)	Date Drug Started (dd/mm/yy)	Date Drug Stopped (dd/mm/yy)	Indication for Treatment

Has the infant had any abnormal screening tests? Yes No If yes, please explain:

Has the infant followed growth curves and developmental milestones as expected for chronological age?

Yes No If no, please explain:

Has the infant had any illnesses or persistent health problems? Yes No If yes, please explain:

Section 4 – Reporter Signature

Signature of person completing questionnaire: _____ Date: _____

Please print name: _____ Title and specialty if HCP _____

Approval Signatures

Document Name: Protocol-Published Original Evolocumab 20200408

Document Description:

Document Number: CLIN-000272100

Approval Date: 16 Jul 2021

Type of Study Protocol: Original

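### Infant growth and milestones at 6 and 12 months are judged against chronological age, so preterm infants on track for their gestation can be counted as infant adverse events

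*Protocol*

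**What the plan says.** Infant adverse events over the first year are part of the primary objective (Section 7.1). Section 8.2.5 sets the assessment times: "Additional follow-up will occur when the infant is 6 and 12 months of age". Section 8.3.2 states that the outcomes at those times "may include whether they have not followed growth curves or met development milestones as expected for chronological age", and the Variables part of the abstract repeats it: "not followed growth curves or met development milestones as expected for chronological age". The infant form in Appendix E puts it to the reporter as a yes/no item: "Has the infant followed growth curves and developmental milestones as expected for chronological age". A 'No' calls for an explanation in free text.

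Premature delivery is a separate outcome in Section 8.3.2: "Premature delivery defined as live birth prior to 37 weeks gestation as counted from LMP". Section 8.7.2.3.3 gives it its own proportion and interval: "fetal death/ stillbirths and premature delivery will be presented, along with corresponding 95% confidence". For the infants, the same section plans one overall figure per time point: "The proportion of infants with adverse events at 6 months and 12 months of age will be assessed".

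The tabulations in Section 8.7.2.3.3 are by consent status, timing of exposure and indication. Gestational age at birth is not among them. Subgroup and stratified analyses (Sections 8.7.2.4.1 and 8.7.2.4.2) are marked as not applicable. Gestational age is nevertheless collected: Appendix D has a field beginning "Weeks of pregnancy at delivery (or if the outcome was a", and Appendix C has the same field.

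**The concern.** Chronological age runs from birth. An infant born eight weeks early has had eight weeks less development at the 6-month form than a term infant of the same chronological age. A reporter who takes the question literally may answer 'No' for an infant who is exactly where its gestation would put it. If that answer is classed as an adverse event, the infant enters a primary proportion for a reason that is not growth or developmental harm.

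This is the only item on the infant form about growth or development. The other health items ask about medications, screening tests, and illnesses or lasting health problems. There is no comparison group (Section 8.7.5.1.4) to show that an excess follows from early birth, and physician adjudication is specified only for major malformations (Section 8.3.2). Section 8.7.2.3.3 allows findings to be escalated as a safety signal towards labelling changes. An analysis plan cannot wholly repair the point, because the wording of the form shapes the answer that is recorded.

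**Working it through.** **No figure to reproduce.** The protocol gives no sample size, expected rate or precision for the infant outcomes.

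**Step 1: the age gap.** Inputs from the protocol are the 6- and 12-month assessments (Section 8.2.5) and the 37-week limit for prematurity (Section 8.3.2). Two assumptions are mine: term is 40 weeks, and a healthy preterm infant develops in line with age counted from term rather than from birth.

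Corrected age in weeks = chronological weeks − (40 − gestational weeks at birth). Six months is 6 × 365.25/12/7 = 26.1 weeks, twelve months is 52.2 weeks, and one month is 4.35 weeks. For a birth at 32 weeks, 26.1 − 8 = 18.1 weeks, and 18.1/4.35 = 4.2 months. In the same way:

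| Birth at | Gap | Corrected age at 6 months | Below chronological | Corrected age at 12 months | Below chronological |
|---|---|---|---|---|---|
| 36 weeks | 4 weeks | 5.1 months | 15.3% | 11.1 months | 7.7% |
| 34 weeks | 6 weeks | 4.6 months | 23.0% | 10.6 months | 11.5% |
| 32 weeks | 8 weeks | 4.2 months | 30.7% | 10.2 months | 15.3% |
| 28 weeks | 12 weeks | 3.2 months | 46.0% | 9.2 months | 23.0% |

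The gap in weeks is the same at both visits, so as a share of age it halves by 12 months.

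**Step 2: what it could do to the proportion.** Let b be the share of infants counted for any other reason, p the preterm share, and f the share of otherwise healthy preterm infants who are answered 'No' and counted. If b is the same in term and preterm infants,

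observed proportion = b + p(1 − b)f.

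The protocol gives none of the three, so all are assumed.

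- b = 5%, p = 10%: f = 10% gives 0.05 + 0.10 × 0.95 × 0.10 = 5.95%; f = 30% gives 7.85%; f = 50% gives 9.75%; f = 100% gives 14.5%.
- b = 10%, p = 10%: the same values of f give 10.9%, 12.7%, 14.5% and 19.0%.
- Over b = 5–10% and p = 5–20%, the excess is zero at f = 0. At f = 100% it runs from 0.05 × 0.90 = 4.5 points to 0.20 × 0.95 = 19 points.

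The excess falls as b rises. The form also asks about illnesses of any kind, so b for the planned any-event proportion may be well above 10%. At b = 50%, p = 10% and f = 30%, the excess is 0.10 × 0.50 × 0.30 = 1.5 points. Because f is unknown, these figures show how the wording acts on the proportion and do not estimate its effect in this study. The excess cannot be negative under this model.

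**The case against.** The strongest reply is that nothing in the protocol turns a 'No' into an adverse event. Section 8.3.2 only says that growth or milestone failure may be part of the infant outcomes, and a reporter can write in the explanation that the baby came early. Following a growth curve can also be read as keeping to a centile, which a small preterm infant may do. Line listings are planned and gestational weeks are on file, so a careful assessor could see prematurity. All of this stands, and it limits the claim to what can happen. It does not remove the problem, because the protocol has no rule for using the explanation or the gestational weeks, and handling would be case by case.

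A reader might infer that every healthy preterm infant is counted as an adverse event, or that the reporter has no choice but to answer 'No'. The text supports neither. A reader might also infer that one event is scored twice. Premature delivery and infant adverse events are separate proportions that are never summed, and one case may properly appear under both. The overlap concerns interpretation and is partial, since growth and milestones are one component of a broader count.

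There is also a fair point about cost. Appendix E is a sample form, and follow-up runs through the sponsor's routine pharmacovigilance process. The study period starts in July 2015 and the protocol was approved in July 2021, so about six of the ten years precede approval. New wording will leave two versions of the item in one series. That argues for a tabulation that works on both versions, alongside the change of wording.

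**Conclusion.** The point holds in a limited form. All three places that define or collect this outcome use chronological age, make no allowance for prematurity and plan no term/preterm split. A preterm infant on track for gestation can therefore enter the infant adverse-event proportion, and that proportion can partly reflect premature delivery. The age gap is material at 6 months for early births and smaller for late preterm births and at 12 months. That conclusion rests on the 40-week reference and on development following corrected age. The protocol does not show how many infants would be affected, and no percentage of inflation should be quoted as a finding. This is an improvement worth making at low cost; it does not undermine the study as a whole.

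**What to change.** 1. For infants born before 37 weeks, classify growth or milestone failure at 6 and 12 months on age corrected for prematurity. Use the gestational weeks recorded in Appendix C or D and the free-text explanation of a 'No'.
2. Change the wording in Section 8.3.2, the abstract and Appendix E to match, for forms sent from then on. Asking the reporter to count age from the due date if the baby was born before 37 weeks would spare lay reporters a calculation.
3. For all forms, including those already returned, tabulate 'No' answers on this item separately for births before 37 weeks and at or after 37 weeks.

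No new data field is needed. The costs are a protocol change, which Section 11.1 makes subject to FDA review and agreement, and a mixed series: answers on the old wording cannot be fully converted, because a bare 'No' without a useful explanation does not show whether the infant was behind for corrected age. The split at 37 weeks covers those forms as far as they allow.

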8.3.3 Covariate Assessment

8.3.3.1 Pregnancy Information

Variables related to pregnancy such as demographics (age); pregnancy history; medical history; current medication and dates of use (prescription and OTC); other relevant history (family history, mother's occupation), and occurrence and dates of pregnancy complications.

8.3.3.2 Post Due Date Birth Information

Variables related to pregnancy and delivery such as maternal conditions, newborn complications, birth information, and delivery details.

8.3.4 Validity and Reliability

The primary exposure variable of exposure during pregnancy is based on maternal, other family member, or HCP report. The outcome variable of adverse events at birth including complications, medical problems or congenital anomalies is based on maternal or HCP report. Adverse events reported at 6 months and 12 months are based on follow-up received from the pregnant woman or HCP. For other outcome variables, standard methods are used to classify the outcome, confirm reliability of data capture, data entry and classification.

8.4 Data Sources

The Amgen Global Safety Database is a comprehensive pharmacovigilance database that contains reports of adverse event data for all Amgen products including Repatha and all safety reports from clinical and post market sources. Amgen performs follow-up on adverse events reported for all products including Repatha as per Amgen's due diligence process. The Amgen Global Safety Database includes reports of pregnancy, birth outcome, and infant health information of women who have had direct exposure to Repatha prior to or during pregnancy. Pregnant women may or may not provide consent for their health and their children's health information to be obtained by Amgen. The database contains positive and negative pregnancy outcome data, including congenital

anomalies, spontaneous and elective abortions, fetal death/stillbirths, and premature birth.

All Repatha pregnancy cases (which may include multiple pregnancies from the same woman), of which Amgen becomes aware, reported from the postmarketing experience (including through spontaneous reporting, cases solicited through patient support programs, market research, from the literature, from regulatory authorities, or postmarketing non-interventional studies) are entered into the Amgen Global Safety Database. Pregnancy exposure case reporting and follow-up through the infant's first year of life is voluntary and participants are free to withdraw at any time.

Amgen does not provide compensation for participation in the follow-up process. Participants are required to provide verbal or written consent that allows Amgen to collect relevant pregnancy, birth outcome, and infant health information.

As per Amgen's due diligence process, upon notification of a Repatha exposure during pregnancy (with or without an adverse event), Amgen Global Patient Safety follows up with the reporter to request informed consent to obtain pregnancy and infant health information from the mother. Follow-up will be performed as per Amgen's routine pharmacovigilance process at predefined intervals and adjusted accordingly depending on whether the mother is pregnant or has already delivered. Information requested may include, but is not limited to, alternate contact information for the mother, such as contact information of a close relative or friend, pregnancy/delivery details, medical history, laboratory and diagnostic tests, and HCP names. The process includes a set number of follow-up attempts over predefined intervals (post birth, when the infant is 6 months and 12 months). If there is no response to the follow-up attempts the due diligence process is complete and the case is considered lost to follow-up. An exception to this process is when the reporter explicitly states they are not prepared to provide any further information, did not provide consent to follow-up, or refused to provide any additional information about the pregnancy or infant. If this occurs, follow-up is not conducted.

